## **Aims and hypotheses**

## **2.1 Overall research aims**

The overall aim of this study is to estimate the effect of OMT plus auto-monitoring (OMTa) compared to auto-monitoring alone. Moreover, we aim to identify anatomical and behavioural predictors of OMTa adherence.

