## **Outcomes**

The primary end point of the RCT is change in the AHI

Secondary endpoints:

1. Change in the Epworth Sleepiness scale and PROMs in the European Sleep Questionnaire.
2. OMTa adherence
3. Change in other conventional OSA severity indices (oxygen desaturation index, time below 90% saturation, nadir saturation) and change in novel OSA parameters in SAS identified in the development phase of the project.
4. Change in objective and subjective sleep quality (PSG and sleep diary, respectively).
5. Change in physiological parameters assessed by wearables.
6. Change in objective daytime functioning testing (PVT and Stroop test).
7. Change in self-reported self-efficacy as assessed by the PAM.
8. Changes in the Orofacial Myofunctional Evaluation with Scores (OMES).
9. Changes in the IOPI strength and endurance
10. Changes in hyoid position as assessed by a lateral cephalogram
11. Prediction of improvement in SDB severity by objective parameters from a 2D cephalogram obtained at baseline.

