### **6.1 Statistical analysis**

The Kruskal-Wallis test will be used for intergroup comparisons at each time point (T1 and T2). Intragroup comparisons will be performed by the Friedman test.

Inter-examiner agreement of OMT measurements will be determined by intraclass correlation coefficients (ICCs) and weighted kappa coefficient (Kw'). Effect sizes for statistically significant differences between T1 and T2 will be calculated using the Cohen's d statistic.

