### **6.2 Power calculation**

The number in each group is calculated to N=50 based on the results of Guimaraes et al. The AHI was used in the calculation.

Independent samples t-test, two-sided, anticipated effect size (Cohen's d) 0.8 (high), power  $\geq 80\%$ , probability level 5%. This gives a minimal sample size of 26 per group. The expected drop out of patients during the OMTa trial is 25% corresponding to a total of 20 patients. To accommodate for this potential dropout and to have adequate power for subpopulation analysis for gender, the sample size was increased to 100 (50 in each group).

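### Section 6.1 names no primary test and has no between-arm test of change in AHI, so a significant fall within the OMTa arm could be reported as efficacy

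*Combined protocol and SAP*

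**What the plan says.** The aim in section 2.1 is comparative: "The overall aim of this study is to estimate the effect of OMT plus auto-monitoring (OMTa) compared to auto-monitoring alone". Under Outcomes, "The primary end point of the RCT is change in the AHI"; no contrast or test is attached to it.

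Section 6.1 holds the whole efficacy analysis. Between arms: "The Kruskal-Wallis test will be used for intergroup comparisons at each time point (T1 and T2". Within arms: "Intragroup comparisons will be performed by the Friedman test". On effect size: "Effect sizes for statistically significant differences between T1 and T2 will be calculated using the Cohen's d statistic". T1 and T2 are not defined, but are evidently the baseline and the 90-day outcome evaluation.

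Section 6.2 sizes the trial on AHI with a different test: "Independent samples t-test, two-sided, anticipated effect size (Cohen's d) 0.8 (high), power" of at least 80%, at a 5% level. It does not say whether the effect size refers to AHI at T2 or to its change. No section names a primary analysis or a decision rule, or calls the within-arm tests descriptive.

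**The concern.** The endpoint is a change, and the question is a difference between arms. Section 6.1 never puts the two together. Its between-arm tests use AHI levels at each visit, and its tests of change stay inside one arm. A reader who matches the endpoint to the listed tests arrives at Friedman. The effect-size sentence points the same way, because Cohen's d is triggered by a significant difference between time points, not between arms.

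A within-arm test cannot answer the stated aim. Both arms keep the diary, the watch and the app, and any fall in AHI shared by the arms, whether from self-monitoring or regression to the mean, counts in the within-arm test as if it were an effect of OMT. Finding OMTa significant and the waiting list not significant is no comparison of the arms either. What is at stake is whether a claim of benefit over auto-monitoring alone carries the 5% error rate for which the trial was sized.

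**Working it through.** **1. The plan's own figure.** Section 6.2 gives 26 per group for d = 0.8, two-sided 5%, 80% power. Normal approximation: n = 2(1.960 + 0.842)²/0.8² = 24.5, so 25. The exact t-test gives 25.5, so 26, with power 80.7%. One-sided 5% would give 21. The figure therefore reproduces as a two-sided 5% between-arm comparison.

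**2. Inputs for the error rates.** From section 6.2: 50 per arm, or about 37 after 25% dropout (50 × 0.75 = 37.5). Assumed, because the documents give no value: normal data, T1-T2 correlation ρ of 0.5 or 0.7, and a fall δ equal in both arms of 0 to 0.4 SD. OMTa has no effect throughout. Each test is taken at 5%; that level is stated only in section 6.2, and applying it to 6.1 is the natural reading.

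**3. The within-arm test.** With two time points, Friedman's statistic is Q = (2k − n)²/n, where k is the number of patients whose AHI fell. It is significant when Q > 3.84.

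- n = 37: k = 25 gives 13²/37 = 4.57; k = 24 gives 11²/37 = 3.27. At least 25 falls are needed.
- n = 50: k = 32 gives 14²/50 = 3.92; k = 31 gives 12²/50 = 2.88. At least 32 falls are needed.

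Each patient's chance of a fall is p = Φ(δ/√(2(1 − ρ))), and k is binomial(n, p). The chance of a significant improvement in the OMTa arm is:

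| Common fall (SD) | n=37, ρ=0.5 | n=37, ρ=0.7 | n=50, ρ=0.5 | n=50, ρ=0.7 |
|---|---|---|---|---|
| 0 | 2.4% | 2.4% | 3.2% | 3.2% |
| 0.1 | 6.6% | 8.7% | 10.0% | 13.1% |
| 0.2 | 15.3% | 22.9% | 23.5% | 34.6% |
| 0.3 | 29.3% | 44.9% | 43.5% | 62.6% |
| 0.4 | 47.3% | 68.5% | 65.2% | 84.9% |

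Simulation agrees to within about one percentage point (6-13%, 15-34%, 29-63% and 48-84% for the four non-zero falls).

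**4. Arms that appear to differ.** Let a be the table value and s the chance that the waiting-list test is significant in either direction. OMTa improves significantly and the waiting list does not with probability a(1 − s): 13-23% at 0.2 SD and 21-25% at 0.3 SD.

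**5. No drift, either test accepted.** A two-sided 5% test favours OMTa by chance in 2.5%. Treating the T2 test and the OMTa within-arm test as independent gives 1 − 0.975 × (1 − 0.0235) = 4.8% at 37 per arm and 1 − 0.975 × (1 − 0.0325) = 5.7% at 50. Simulation, which allows for their dependence, gives 4.6-5.7%.

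**6. Between-arm tests.** An equal fall cancels when arms are compared. Over 20,000 simulated trials per setting, the two-sided false-positive rate of a between-arm test, on T2 level or on change, was 4.7-5.3%.

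**The case against.** The strongest reply is that the plan already contains a valid test and that its purpose is clear. Under randomisation, Kruskal-Wallis at T2 holds about 5% whatever drift the arms share. The aim is comparative, section 6.2 uses a two-sided between-arm test on AHI, analysis is by intention to treat, and 6.1 lists the between-arm comparison first. No section says that a within-arm fall will be read as efficacy. All of this stands. It shows intent, but does not bind the analysis, and the T2 test is on levels while the endpoint is change.

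A reader might also infer that four 5% tests on AHI raise the false-positive rate to 1 − 0.95⁴ = 18.5% (16-20% by simulation). The documents do not support that as an efficacy error rate. It counts the T1 comparison, which says nothing about efficacy, the waiting-list within-arm test, which nobody would report as an OMTa effect, and significant worsening. The fair figure without drift is that in step 5. Part of even that excess at 50 per arm comes from the chi-square cut-off: the two-sided size of the within-arm test is 6.5% there and 4.7% at 37.

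Finally, the larger figures rest on an assumed common fall. Nothing in the documents says that a diary, watch or app lowers AHI. That is correct, and it is why the whole range from 0 to 0.4 SD is shown.

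**Conclusion.** The point holds as a missing decision rule together with a mismatch between endpoint and tests. Section 6.1 does not say which result decides whether OMTa works, and it lists no between-arm test of the primary endpoint.

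Without drift the consequence is modest: a false claim for OMTa at about twice the rate of a single test. With a shared fall it grows quickly, because the within-arm test responds to the fall and the between-arm test does not. The sizes depend on the assumed correlation, normality and common fall; the direction does not.

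It would go too far to say that the plan lacks any valid comparison of the arms, or that the investigators intend to claim efficacy from a within-arm result. The documents show neither. The plan should be amended, but the design is sound.

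**What to change.** State in section 6.1 that the single confirmatory analysis is the between-arm comparison, OMTa versus auto-monitoring alone, of change in AHI from T1 to T2 at two-sided 5%, and name one test for it. The independent-samples t-test of section 6.2, applied to change, or its rank equivalent would do. Then add:

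- Efficacy is concluded only from that test.
- The effect size is reported for the between-arm difference, whether or not it is significant.
- Within-arm changes are reported descriptively.
- The significance test at T1 is dropped.

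The amendment should be dated before any comparison of the arms, since choosing the decisive test afterwards cannot restore the 5% rate.

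The cost is a few sentences, with no new data and no more patients. If the planned d = 0.8 applies to change, t-test power is 97.7% with 50 per arm and 92.4% with 37. The downside for the sponsor is that a significant fall within the OMTa arm can no longer be presented as evidence of efficacy.

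### With only T1 and T2, the planned Friedman test is the uncorrected sign test: it ignores the size of each patient's change, and its true level drifts with the number of completers

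*Combined protocol and SAP*

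**What the plan says.** Section 6.1 of the combined protocol and SAP names two tests for outcomes. Between groups: "The Kruskal-Wallis test will be used for intergroup comparisons at each time point (T1 and T2"). Within groups: "Intragroup comparisons will be performed by the Friedman test". It then adds Cohen's d as an effect size for those T1 to T2 differences that reach statistical significance. No other test of change is named.

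Under Outcomes, "The primary end point of the RCT is change in the AHI", and most secondary endpoints are also worded as changes, for example "Changes in the IOPI strength and endurance". Section 6.2 bases the sample size on a two-sided independent-samples t-test with Cohen's d of 0.8: "This gives a minimal sample size of 26 per group", raised to 50 per group for dropout and for analyses by gender. The documents give no SD of change, no T1 to T2 correlation and no within-patient effect size.

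**The concern.** The Friedman test ranks each patient's repeated values. With two values the ranks can only be 1 and 2, so the test keeps whether a patient went up or down and discards by how much. An AHI that falls from 25 to 5 counts the same as one that falls from 25 to 24. AHI, Epworth score, OMES and IOPI are continuous or graded, so this information is available and is thrown away.

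Two things are at stake. True within-arm changes may be missed that a test using their size would detect. And because Cohen's d is tied to significant T1 to T2 differences, the same test appears to determine which effect sizes reach the report.

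**Working it through.** **Inputs.** Two time points and the Friedman test (section 6.1). 50 per arm and 25% dropout (section 6.2), which leaves 50 × 0.75 = 37.5, so 37 or 38 completers per arm. Section 6.2 also equates this dropout with 20 patients in total; split evenly, that leaves 40 per arm. The standardised within-patient change dz (mean change divided by SD of change) is not given and is assumed here.

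**The plan's own figure.** For d = 0.8, two-sided 5% and 80% power, the normal approximation is 2 × (1.96 + 0.84)² / 0.8² = 24.5, so 25. The exact noncentral-t solution is 25.52, so 26 per group, with power 0.807. The plan's 26 is reproduced. It is a between-arm figure and says nothing about the Friedman test.

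**Step 1, the identity.** Let k of n patients improve, with no ties. The Friedman statistic for two columns is Q = (2k − n)² / n, referred to chi-square with 1 df (critical value 3.84). That is the sign test without continuity correction. Example: n = 37, k = 25 gives (50 − 37)² / 37 = 169 / 37 = 4.568, the value the Friedman routine returned. With ties, Q is (n₊ − n₋)² / (n₊ + n₋), again the sign test.

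**Step 2, the true level.** With no change, k is binomial(n, 0.5), and Q takes few values near 3.84:

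- n = 37: rejects at k ≤ 12 or k ≥ 25 (Q = 4.57; the next value inward is 3.27). Level 4.7%.
- n = 38: rejects at k ≤ 12 or k ≥ 26 (Q = 5.16; next 3.79). Level 3.4%.
- n = 40: rejects at k ≤ 13 or k ≥ 27 (Q = 4.90; next 3.60). Level 3.8%.
- n = 50: rejects at k ≤ 18 or k ≥ 32 (Q = 3.92; next 2.88). Level 6.5%.

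**Step 3, power under assumed normal changes.** The probability that a patient improves is Φ(dz): 0.655 at dz 0.4, 0.691 at 0.5 and 0.788 at 0.8. Friedman power is the binomial probability of the rejection regions above. Signed-rank power is by simulation (20,000 to 40,000 runs per setting).

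| n per arm | dz | Friedman (%) | Signed-rank (%) | Loss (points) |
|---|---|---|---|---|
| 37 | 0.4 | 47.3 | 63.8 | 16.5 |
| 37 | 0.5 | 65.7 | 82.2 | 16.5 |
| 37 | 0.8 | 96.4 | 99.6 | 3.2 |
| 38 | 0.4 | 42.7 | 64.8 | 22.1 |
| 38 | 0.5 | 61.5 | 83.3 | 21.8 |
| 38 | 0.8 | 95.6 | 99.6 | 4.0 |
| 50 | 0.4 | 65.2 | 77.6 | 12.4 |
| 50 | 0.5 | 82.7 | 92.4 | 9.7 |
| 50 | 0.8 | 99.5 | 100.0 | 0.5 |

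At n = 40 the losses are 20.3 (dz 0.4), 19.4 (dz 0.5) and 2.9 (dz 0.8), inside the same range. Part of the smaller loss at n = 50 comes from the 6.5% level. The exact sign test there, at level 3.3%, has power 53.8% and 74.1% at dz 0.4 and 0.5, losses of 23.8 and 18.3 points.

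**Step 4, other shapes.** For Laplace changes at n = 37 and dz 0.4, Friedman has 76.9% and signed-rank 77.3%: no real loss. At n = 50 and dz 0.3 the order reverses, 74.5% against 68.8%. For t changes with 5 df at n = 37 and dz 0.4, it is 62.6% against 72.9%, a loss of 10.3 points.

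**Step 5, reading two within-arm tests side by side.** If both arms change equally and each within-arm test has power p, the chance that OMTa is significant and the waiting list is not is p(1 − p). For Friedman at n = 37, p = 0.152, 0.29 and 0.475 (dz 0.2, 0.3 and 0.4, simulated) give 0.13, 0.21 and 0.25. Signed-rank does not cure this: at dz 0.4 it gives 0.638 × 0.362 = 0.23.

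**The case against.** The strongest reply is that this is a matter of efficiency in a secondary comparison. The stated aim is OMTa plus auto-monitoring against auto-monitoring alone, a between-arm question, and the sample size rests on a between-arm test. If within-arm results are descriptive, as they should be, their power matters less. That stands, and it limits the importance of the point. It does not make the test suitable: section 6.1 does not call the within-arm tests descriptive, and it attaches effect-size reporting to T1 to T2 significance.

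Four stronger readings are tempting, and the documents do not support them:

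- **A fixed loss of power.** A reader might take one figure, say 13 to 17 points, as the cost. That needs a within-patient effect size, a distribution and a completer count, and the documents give neither of the first two. The 0.8 in section 6.2 is a between-group d. It does not establish dz = 0.8, at which the loss would be small, any more than it establishes 0.4.
- **A patient-equivalent cost.** One might infer that Friedman with 50 patients matches signed-rank with 37 at dz 0.5 (82.7% against 82.2%). The comparison is unfair because Friedman then runs at a 6.5% level. About 56 patients are needed for similar power (82.5%), at a level of 4.4%.
- **An underpowered trial.** The between-arm calculation in section 6.2 does not use the Friedman test and is unaffected.
- **An invalid test.** A sign-type test is a legitimate test of direction. Some software refuses fewer than three samples (scipy does), but that is a restriction of the routine.

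Scope is also limited. The app cognitive tests are requested three times in the 90 days, and PVT and Stroop are secondary endpoints; with three values Friedman is not degenerate. Polysomnography covers three nights on each of two occasions. Entering the nights separately would also escape the identity, but section 6.1 describes only T1 and T2.

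**Conclusion.** The point holds for within-arm comparisons of outcomes with one value at T1 and one at T2. That the test reduces to the uncorrected sign test, and that its level moves between 3.4% and 6.5% over 37 to 50 completers, follows from the algebra and the binomial distribution with no assumption about effect size.

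The power loss is conditional. With normal changes and 37 to 50 patients per arm it is about 10 to 22 points against signed-rank at an assumed dz of 0.4 to 0.5, and at most about 4 points at 0.8. It can disappear or reverse with heavy-tailed changes. The plan should be changed, because the stated test is a poor match for graded outcomes and the correction is trivial. The main between-arm comparison is not undermined by this point.

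**What to change.** In section 6.1, replace the Friedman test by the Wilcoxon signed-rank test for T1 to T2 change within arm, or by a paired estimate of change with its 95% CI. Add that within-arm results are descriptive, and that significance in one arm but not in the other is not evidence of a treatment effect. If outcomes with three measurements are to be tested within arm, name their method separately.

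The cost is a sentence or two in section 6.1, with no new data. This change does not supply a between-arm analysis of change in AHI: the Kruskal-Wallis test compares levels at each time point, and that gap needs its own correction.

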#### **After baseline evaluation:**

##### *Polysomnography (PSG)*

All patients, both intervention and waiting list group, will administer three nights of self-applied PSG (hereinafter called SAS). This is an alternative to in-lab services and PSG setups, in a self-applied form. The EEG is located only on the forehead (F-channels), with no electrodes located on the top of the scalp (C-channels) and back of the head (O-channels) as in traditional PSG. The self-applied setup facilitates

the use of multi-night studies to capture night-to-night variability and the participants apply the sensors themselves, using an instructional video provided by Nox. In this study, we will do three nights in a row twice. PSG will be performed before the baseline consultation and before the outcome evaluation. The equipment will be given out at baseline consultation. After use the patients will mail the equipment back to Ahus/FPH or bring the equipment back to the first treatment session.

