### Stroop test

The Stroop test is a frequently used test for measuring inhibitory control, selective attention, and cognitive flexibility. It requires the subject to inhibit an unwanted response, and direct the attention to the task-specific goal. The test consists of three parts: In the first part, the subject is asked to read the words "green", "red", "blue", and "yellow" and the reading speed is measured. In the second round, the

colors are presented as blocks and the participant needs to name the correct color. In the last part, a color word is presented in another color, creating an incongruent condition. Here, the participant is instructed to name the color of the word and suppress naming the written word. Reliability and validity of this test are good. In the context of sleep disorders, the Stroop test showed worse performance in patients with OSA and insomnia and is therefore a good addition to this study. This test will be available in the app.

The completion of the tests will be voluntary in this study. Participants will be asked to perform the tests three times during the 90 day study period.

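### The stated aim is to estimate the effect of OMTa against auto-monitoring alone, but the plan commits to no between-arm effect estimate and no confidence interval

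*Combined protocol and SAP*

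**What the plan says.** Section 2.1 gives the purpose: "The overall aim of this study is to estimate the effect of OMT plus auto-monitoring (OMTa) compared to auto-monitoring alone". The Outcomes section adds: "The primary end point of the RCT is change in the AHI".

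Section 6 and section 6.1 contain the whole analysis text. For the comparison of arms, section 6.1 says "The Kruskal-Wallis test will be used for intergroup comparisons at each time point (T1 and T2". Within each arm it names the Friedman test. It also plans ICCs and a weighted kappa, which measure agreement between examiners. The only effect-size output is introduced by "Effect sizes for statistically significant differences between T1 and T2 will be calculated", using Cohen's d. Section 6 adds that the analysis is by intention to treat.

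Section 6.2 does contain a between-group effect size, "anticipated effect size (Cohen's d) 0.8 (high", but as a planning input to the sample size and not as something to be reported.

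**The concern.** A Kruskal-Wallis test yields a p-value. It does not say how much lower AHI is in the OMTa arm or how precisely that is known. An aim to estimate therefore needs an estimate and an interval, and neither is planned for any endpoint.

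The planned Cohen's d does not fill the gap. Section 6.1 itself calls T1 and T2 time points, so a difference between them is a change over time. Such a change includes whatever the two arms share: regression to the mean, the effect of self-monitoring (both arms have it), and night-to-night variation in the sleep recordings. If both arms improved equally, the within-arm d would be positive while the OMTa effect was zero. The plan does not call this d the treatment effect, but it offers nothing else.

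Reporting d only after a significant result adds a second, smaller problem. Where true effects are small, only the larger observed values pass the filter, and non-significant endpoints are left with no estimate at all.

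**Working it through.** **Inputs.** From section 6.2: two-sided independent-samples t-test, d = 0.8, 5% level, power at least 80%, 26 per group as the minimum, 50 per group as the target. On dropout it says "The expected drop out of patients during the OMTa trial is 25% corresponding to a total of 20 patients". Three arm sizes follow: 50 (no loss), 40 (the 20 patients split evenly) and 37 (50 × 0.75 = 37.5, rounded down).

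**The plan's own figure.** The t-test calculation with d = 0.8 gives 25.5 per group, rounded up to 26, with power 80.7% at 26. The stated minimum reproduces and is not in dispute.

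**Search for a between-arm estimate.** Reading the whole document against the aim:

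| Planned output | Compares arms? | Gives size of effect? | Gives interval? |
|---|---|---|---|
| Kruskal-Wallis at T1 and at T2 | yes | no | no |
| Friedman within arm | no | no | no |
| Cohen's d, T1 to T2, if significant | no | yes, within arm as worded | no |
| ICC, weighted kappa | no (rater agreement) | no | no |

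The tests between arms are also placed at each time point separately, so no between-arm analysis of change, the primary endpoint, is named.

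**Precision the plan leaves unreported.** For an observed between-arm d of 0.8, the approximate 95% interval is 0.8 ± 1.96 × √(2/n + 0.8²/(4n)).

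- n = 50: √(0.0400 + 0.0032) = 0.208; half-width 0.407; interval 0.39 to 1.21
- n = 40: √(0.0500 + 0.0040) = 0.232; half-width 0.455; interval 0.34 to 1.26
- n = 37: √(0.0541 + 0.0043) = 0.242; half-width 0.474; interval 0.33 to 1.27

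Even at the planned effect, the data would be compatible with anything from a modest to a very large benefit. A p-value alone does not show this.

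**The significance filter.** Simulation with 2,000,000 runs per cell. Assumptions: normal T1–T2 differences; d = mean divided by SD of the differences (section 6.1 gives no denominator); two-condition Friedman test, chi-square with 1 df, at 0.05. True values of 0.2 to 0.4 are assumed, since the document gives no within-arm effect; 0.8 borrows the figure from section 6.2. Entries are probability of significance / mean d over all trials / mean d when significant.

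| True d | n = 50 | n = 40 | n = 37 |
|---|---|---|---|
| 0.2 | 0.236 / 0.203 / 0.355 | 0.144 / 0.204 / 0.413 | 0.156 / 0.205 / 0.416 |
| 0.3 | 0.436 / 0.305 / 0.413 | 0.284 / 0.306 / 0.468 | 0.294 / 0.306 / 0.472 |
| 0.4 | 0.653 / 0.406 / 0.474 | 0.469 / 0.408 / 0.524 | 0.473 / 0.409 / 0.529 |
| 0.8 | 0.995 / 0.813 / 0.814 | 0.969 / 0.816 / 0.826 | 0.965 / 0.817 / 0.829 |

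At 0.8 the filter adds at most about 0.2% (n = 50), 1.2% (0.826/0.816) and 1.5% (0.829/0.817). At 0.2 the reported mean is roughly 1.75 to 2 times the unfiltered mean (0.355/0.203 and 0.416/0.205).

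With two time points the Friedman test is a sign test, and its chi-square version is discrete. Its true size under no change is 6.5% at n = 50, 3.8% at n = 40 and 4.7% at n = 37. That is why the probability of significance at d = 0.2 is slightly lower at 40 than at 37. With an exact sign test the n = 50 means for 0.2, 0.3 and 0.4 become about 0.385, 0.438 and 0.496; those at 40 and 37 do not change.

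**The case against.** Four points can be made for the plan.

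1. The wording of the effect-size sentence names no arm, and section 6.2 uses Cohen's d between groups, so the sentence might mean the arm difference in T1–T2 change. This is possible but strained, because the same section defines T1 and T2 as time points. Even so read, the d would still depend on significance and have no interval.

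2. The authors may well report an estimate anyway. But the plan does not say whether it would be a difference at T2 or in change, a mean or a median, adjusted or not. Those choices should not be left until the data are seen.

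3. The intervals above follow from the sample size and would be just as wide if the plan promised to report them. This is correct. They show what would go unreported and do not measure a bias. They also describe an unadjusted standardised difference, not an adjusted difference in AHI units.

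4. The filter hardly matters at the only effect size in the document, and the larger inflation rests on assumed values. This is also correct, and it is why the filter is secondary here. The direction of the bias for small effects stands.

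Baseline adjustment is a recommendation and not the only remedy. An unadjusted or rank-based difference with an interval would also close the gap.

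**Conclusion.** The concern holds. The plan states an estimation aim and provides, for the arm comparison, only tests at T1 and at T2. No between-arm effect estimate or confidence interval is planned anywhere, and the single effect-size output is conditional on significance and, as worded, concerns change over time. This rests on the text alone and needs no assumption about the data.

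It should be corrected, but it does not invalidate the trial: the AHI data needed for the estimate are to be collected in both arms. The filter is negligible if within-arm effects are near 0.8 SD. It matters only for endpoints with small effects, under the stated assumptions of normal differences and d scaled by the SD of the differences.

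**What to change.** Replace the effect-size sentence in section 6.1 with text such as:

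> For the primary endpoint, and for each secondary endpoint with a defined baseline and outcome value in both arms, we will report the difference between arms (OMTa minus waiting list), adjusted for the baseline value, with its 95% confidence interval, regardless of the p-value. The adjusted difference in AHI is the primary effect estimate. Within-arm effect sizes are descriptive, given for both arms without a significance filter, and the denominator of Cohen's d is stated.

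If a rank test is kept as the primary test, add a Hodges-Lehmann shift in AHI change with its 95% confidence interval, and one sentence on how test and estimate relate.

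Name the recording nights that supply baseline AHI. The section on polysomnography says "PSG will be performed before the baseline consultation and before the outcome evaluation. The equipment will be given out at baseline consultation"; these two timings must be reconciled.

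The rule does not apply to OMTa adherence (the waiting list cannot open the treatment module) or to prediction from the cephalogram. Some endpoints come under it only once their baseline and outcome values are defined. Examples are the voluntary cognitive tests ("Participants will be asked to perform the tests three times during the 90 day study period"), wearable data, the diary's outcome window, the PAM (not among the listed baseline measures) and the repeat cephalogram (not in the outcome-visit list). The list is not exhaustive: the European Sleep Questionnaire has no schedule of its own, and the novel sleep parameters are still to be identified.

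The cost is a few table columns and a short paragraph. No new data are needed for AHI.

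### Section 6.1 plans effect sizes for significant T1–T2 differences and no between-group estimate, so modest effects will be overstated and the trial's stated aim of estimation is not served

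*Combined protocol and SAP*

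**What the plan says.** Section 2.1 states the aim as estimation of a between-group effect: "The overall aim of this study is to estimate the effect of OMT plus auto-monitoring (OMTa) compared to auto-monitoring alone". The Outcomes section adds: "The primary end point of the RCT is change in the AHI". It then numbers 11 secondary items. Nine of them are changes; the other two are OMTa adherence (item 2) and prediction from the baseline cephalogram (item 11).

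Section 6.1 supplies the analysis. Between groups it names a Kruskal-Wallis test at each time point. Within groups: "Intragroup comparisons will be performed by the Friedman test". On magnitude it has one sentence: "Effect sizes for statistically significant differences between T1 and T2 will be calculated", with Cohen's d as the statistic. The only other statistics it names are intraclass correlation and weighted kappa, which concern agreement between examiners.

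Section 6.2 plans the sample size on a two-sided independent-samples t-test with a Cohen's d of 0.8, at least 80% power and a 5% level.

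**The concern.** The sentence on Cohen's d is the plan's only provision for the size of an effect, and significance is the condition for applying it. Three problems follow.

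- An estimate that is calculated only after it has passed a significance test is too large on average, because the low estimates are the ones that fail the test.
- A change endpoint that misses significance has a planned test but no planned effect size or interval. A reader could not tell a precise null from an uninformative one.
- T1 and T2 are time points, so the d in this sentence describes change over time, not OMTa against auto-monitoring. The contrast named in section 2.1 has a test and no planned estimate.

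The secondary change endpoints are the most exposed. Section 6.2 powers the trial on AHI alone, and nothing in the documents says that the secondary effects will be large.

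**Working it through.** **The plan's own figure.** Section 6.2 gives 26 per group. The normal approximation is n = 2(1.960 + 0.842)²/0.8² = 15.70/0.64 = 24.5, rounded up to 25. The exact t-test solution is 25.52, rounded up to 26. The figure reproduces, and this point does not affect it.

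**Inputs from the documents.** The Friedman test with two time points (6.1); Cohen's d given significance (6.1); two-sided 5% (6.2); 50 per arm (6.2); 25% dropout (6.2), giving 50 × 0.75 = 37.5, taken as 37.

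**Assumptions.** Changes are normal. d is the mean change divided by the SD of change. The true values 0.2 to 0.5 are assumed. The value 0.8 is borrowed from section 6.2, where it is a between-group figure.

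**Test rule.** With two time points and no ties, Friedman's statistic is Q = (2k − n)²/n, where k is the number of patients whose change is positive. It is significant when Q > 3.84.

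- n = 37: |2k − 37| must exceed √(3.84 × 37) = 11.9, so k ≥ 25 or k ≤ 12.
- n = 50: |2k − 50| must exceed √(3.84 × 50) = 13.9, so k ≥ 32 or k ≤ 18.

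**Simulation.** At least 40,000 trials per setting. Reported d is the mean of d over the significant trials only.

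| True d | n=37: significant | n=37: mean d, all trials | n=37: mean reported d | n=50: significant | n=50: mean d, all trials | n=50: mean reported d |
|---|---|---|---|---|---|---|
| 0.2 | 15% | 0.20 | 0.42 | 24% | 0.20 | 0.36 |
| 0.3 | 29% | 0.31 | 0.47 | 44% | 0.30 | 0.41 |
| 0.4 | 47% | 0.41 | 0.53 | 65% | 0.41 | 0.47 |
| 0.5 | 66% | 0.51 | 0.59 | 83% | 0.51 | 0.54 |
| 0.8 | 96% | 0.82 | 0.83 | 99.5% | 0.81 | 0.81 |

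Reported d divided by true d, in row order:

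- n = 37: 0.42/0.2 = 2.1, 0.47/0.3 = 1.6, 0.53/0.4 = 1.3, 0.59/0.5 = 1.2, 0.83/0.8 = 1.04.
- n = 50: 0.36/0.2 = 1.8, 0.41/0.3 = 1.4, 0.47/0.4 = 1.2, 0.54/0.5 = 1.1, 0.81/0.8 = 1.01.

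At 0.8 most of that small excess is the ordinary small-sample bias of d. The filter itself adds about 1% at n = 37 (0.82 to 0.83) and almost nothing at n = 50.

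At true d = 0.2 and n = 37, about 85% of trials would have no effect size for that comparison. With no true change, the few values that are reported average |d| of 0.33 (n = 37) or 0.26 (n = 50).

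**If the same filter were carried over to the between-group comparison.** With the Kruskal-Wallis test and n = 37, true values of 0.2, 0.3, 0.5 and 0.8 would be reported as 0.56, 0.60, 0.68 and 0.85. The condition must therefore not be kept when a between-group estimate is added.

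**The case against.** The best defence is that the rule changes no test, no sample size and no p-value, and that it is nearly harmless at the only effect size in the documents. That stands: at 0.8 the filter adds about 1% or less. The bias also shrinks when more patients are analysed, which is why 50 per arm is shown beside 37. Section 6.2 equates its 25% dropout with 20 patients. Losing 20 of 100 would leave 40 per arm, and the results there are within 0.01 of those at 37.

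Four stronger readings are tempting, and the documents do not support them.

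- A reader might infer that every reported size exceeds the truth. The bias is an average. At a true 0.8, about 47% of the significant estimates at n = 37 still fall below 0.8.
- A reader might infer that the rule covers every endpoint. It concerns T1–T2 differences, so adherence and cephalogram prediction lie outside it.
- A reader might infer that null results will be published with no magnitude at all. The word *only* is not in the sentence, and section 6.1 does not rule out descriptive summaries. What is missing is any planned effect size or interval for them.
- A reader might infer that the reported d is inflated by its scale relative to the planning 0.8, or could be put on that scale by choosing a denominator. The documents state neither a denominator nor a baseline-to-outcome correlation, so no such factor can be derived. A within-arm d also includes any change that occurs on the waiting list, so no denominator turns it into the between-group quantity of section 6.2.

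**Conclusion.** The point holds for T1–T2 change endpoints. The rule gives effect sizes that are too large on average, and it plans none for non-significant changes. For true within-arm effects of 0.2 to 0.3 the average overstatement is about 1.6 to 2.1 times at 37 per arm and 1.4 to 1.8 times at 50. It falls to 1.1 to 1.2 times at 0.5 and is negligible at 0.8. These figures rest on normal changes and assumed true effects; the documents do not give the size of any secondary effect.

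The lack of a planned between-group estimate depends on none of these assumptions and conflicts directly with section 2.1. The trial's tests and sample size are unaffected. This should be corrected before analysis, but it does not undermine the trial.

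**What to change.** Replace the sentence on Cohen's d in section 6.1 with a rule of this kind: *For the primary endpoint and every secondary change endpoint, the between-group effect (OMTa minus auto-monitoring) will be reported with a 95% confidence interval, whatever the p-value.* Name the estimator in advance.

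If within-arm T1–T2 effect sizes are kept, label them descriptive, state their denominator, and report them for all change endpoints regardless of significance. Removing the significance condition alone is not enough, because what remains would still be a within-arm quantity and would not answer section 2.1.

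The cost is one sentence in section 6.1 and some extra table rows. No patients, visits or data are added.
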